4.6 LOST TO FOLLOW-UP

Subjects who miss at least two consecutive visits, as defined by the visit windows and cannot be contacted, may be considered lost to follow-up. All follow-up attempts will be documented and kept with the subject's source documentation, and the applicable eCRFs will be completed.

Subjects that voluntarily withdraw consent after implantation with the HMIOL will be considered Lost to Follow-Up.

4.7 STUDY COMPLETION

ClarVista will notify the Investigators when to contact the IRB / EC to announce study completion at the site.

CLARVISTA MEDICAL

PROTOCOL CP-00001 Rev.05

4.7.1 EARLY STUDY TERMINATION

ClarVista has the right to terminate this study at any time. Reasons for terminating the study may include, but are not limited to, the following:

- The incidence or severity of adverse events in this or any ongoing studies involving the same technology (if applicable), indicates a potential health hazard to subjects
- Subject enrollment is unsatisfactory
- Data recording is inaccurate or incomplete.
- A minimum of 105 subjects has been enrolled in the study *and* a minimum of 44 optic exchanges has taken place.

In the event of premature study termination, appropriate notification will be given to the Investigators, IRB / ECs, and regulatory bodies as applicable. In addition, ClarVista (or designee) will instruct all Investigators to discontinue dispensing study materials or treatments, will ensure all subjects complete appropriate follow-up, and will arrange study closeout visits at each site as appropriate.

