
Sample Size
	
The sample size of this feasibility study is first calculated based on ISO 11979-7:2014 (E) to evaluate the proportion of HMIOL-implanted eyes with BCDVA of 0.3 logMAR of better for all HMIOL Cohort (post optic exchange for HMIOL Cohort 2). The statistical hypotheses for the effectiveness are $H_0: p \geq 0.925$ and $H_a: p < 0.925$, where p is the proportion of HMIOL-implanted eye with BCDVA of 0.3 logMAR. Based on the binomial distribution with a one-side significance level of 0.05 and a true p of 0.85, a sample size of 100 eyes will provide a statistical power of about 75%; while a sample size of 200 eyes will provide a statistical power of about 95%. Therefore, a sample size of 100 to 200 eyes implanted with HMIOL will be required for the study. For any adverse events that are not observed during the study, the one-sided upper 95% confidence limit of the adverse event rate is 0.0362 if the sample size is 100 eyes. The one-sided upper 95% confidence limit of the adverse event rate is 0.0183 if the sample size is 200 eyes. Therefore, a sample size of 100 to 200 deems to be sufficient for evaluating the safety and effectiveness of HMIOL for this feasibility study.
 
[REDACTED] [REDACTED] [REDACTED] [REDACTED]

	
[REDACTED]
 
The goal will be to enroll up to 200 subjects. However, after the first 25 subjects have reached the 3 month time point (and every 25 subjects thereafter), subject accountability and the rate of optic exchanges will be evaluated, and the enrollment goal will be reevaluated with respect to achieving the necessary sample size.
 
It should be noted that this is a feasibility study. All the analyses are to evaluate the effectiveness and safety of the HMIOL for the future confirmatory study. No adjustment is performed for the multiplicity.

--	--

[REDACTED]

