3.3.1 PRE-OPERATIVE VISIT – SCREENING/BASELINE (DAY -90 TO DAY -1)

After providing informed consent (see Section 4.1), prospective subjects will be screened to determine whether they meet enrollment criteria. Demographic information, relevant ocular history, and current ocular medication use will be collected. If all criteria are met, the subject will be considered enrolled, IOL calculation completed to determine appropriate HMIOL power, and the subject scheduled for surgery.

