At the 3 month visit, an overall assessment of a subject's visual function will be performed by the physician. If the physician's assessment results in an opportunity for improved visual function through optic exchange in the test eye, the subject will be offered that opportunity. The Investigator and the Subject will decide if an optic exchange is appropriate.

The decision will be documented and the prospective Cohort indicated.

- If the subject has an acceptable outcome or it is otherwise decided an optic exchange will not take place, the subject will be entered into Cohort 1 and be followed at the 6 and 12 Month Visits prior to study completion. If the subject desires an exchange, however it is decided they cannot have one based on exclusion criteria (Section 3.2.4), the subject will remain in Cohort 1 and can utilize spectacles to correct RRE for the remainder of study participation. The investigator and subject can decide on further treatment per the Investigator's standard of care, following study participation.
- If it is decided an HMIOL optic exchange is desired, the appropriate pre-operative measurements will be obtained, 3 Month Visit assessments completed per Appendix A – Table 1, and HMIOL calculations and optic ordered. Finally, the subject will be scheduled for the procedure and entered into Cohort 2 (finalized after successful completion of optic exchange). If for any reason the optic exchange procedure does not take place, the subject will default back to Cohort 1.

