4.5 SUBJECT DISCONTINUATION

A subject **MUST** be discontinued prior to the final study visit for any of the following reasons:

- Death
- Subject is enrolled and scheduled for surgery but is not implanted with an HMIOL at Day 0 (Operative Visit – Primary Cataract Extraction)
- Surgical complication(s) unrelated to the investigational device preventing the implantation of the HMIOL (i.e. capsulorhexis tear, zonular rupture, evident zonular weakness or dehiscence, posterior capsular rupture, vitreous loss, posterior capsular plaque, significant detached Descemet's membrane, significant anterior chamber bleeding, iris incarceration or damage, corneal endothelial touch, unsuccessful/incomplete phacoemulsification, haptic and/or optic damage/haptic amputation)
- Explantation of the HMIOL System

If the study lens is explanted, one postoperative visit should be completed to record best-corrected distance visual acuity (BCDVA) before the subject is discontinued.

Subjects who withdraw from the study will be asked to complete procedures outlined in the 12 Month Visit (if withdrawn prior to that visit). Subjects who are terminated due to an AE will be followed, if possible, at least until resolution or stabilization of the AE. Subject withdrawals will be documented clearly on the source document and applicable eCRF.

Prior to discontinuing a subject, every effort should be made to contact the subject, schedule a final study visit, and obtain as much follow-up data as possible. Adverse events will be followed as described in Section 6.3.4. Discontinued subjects should be followed outside of the study protocol according to the Investigator's normal postoperative standard of care.

A Study Exit eCRF must be completed for all subjects who discontinue from the clinical investigation.

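### The closing criterion in Protocol 4.7.1 counts enrolled subjects, not implanted eyes, so it can be met with fewer than the required 100 implanted eyes

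*Protocol*

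**What the plan says.** **Closing criterion.** Protocol Section 4.7.1 gives the sponsor a right to terminate at any time and lists possible grounds: "Reasons for terminating the study may include, but are not limited to, the following". One ground has two parts that must both hold: "A minimum of 105 subjects has been enrolled in the study" and "a minimum of 44 optic exchanges has taken place".

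**When a subject becomes enrolled.** Section 3.3.1, the pre-operative visit (Day -90 to Day -1), states: "If all criteria are met, the subject will be considered enrolled, IOL calculation completed to determine appropriate HMIOL power". Surgery comes later.

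**Enrolled but never implanted.** Eligibility is reviewed again on the day of surgery (3.3.2), and 3.2.3 lists seven exclusions during surgery. Section 4.5 makes discontinuation mandatory where "Subject is enrolled and scheduled for surgery but is not implanted with an HMIOL at Day 0". Section 8.2 removes subjects disqualified on pre-operative or intra-operative criteria from the safety and effectiveness analyses.

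**Required size.** The Synopsis (Sample Size) concludes that "a sample size of 100 to 200 eyes implanted with HMIOL will be required for the study". Section 8.1 gives a power of 0.753 at 100, although there the unit is called subjects.

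**Review of the enrolment goal.** Section 4.7.2 reviews accountability and the exchange rate after every 25 subjects reach 3 months, and reconsiders the goal against the sample size needed.

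**Consequence of termination.** Under 4.7.1 the sponsor "will instruct all Investigators to discontinue dispensing study materials or treatments" and will also see that subjects finish appropriate follow-up. Section 6.4 refers back to 4.7.1 as a right to stop enrolment. Section 3.3.4 provides for an offer of exchange at the 3 Month Visit: "If the physician's assessment results in an opportunity for improved visual function through optic exchange in the test eye, the subject will be offered that" (final word omitted).

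**The concern.** The required size is in implanted eyes, but the criterion that signals enough has been collected is in enrolled subjects. The protocol itself provides for people who are enrolled and never implanted, and they remain in the enrolled count. The margin of 5 over 100 has to cover all of them. No readable text in 4.7.1 sets a minimum number of implanted eyes. The sponsor could therefore close the study on this ground, within the protocol, and still miss the protocol's own minimum.

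A second matter is the wording of the consequence. Terminating the study and ceasing to dispense study materials is not the same as stopping enrolment. At any closing date some implanted subjects may still be short of the 3 Month decision on exchange, and the sections do not say clearly what then applies to them.

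**Working it through.** **Inputs.** Protocol 4.7.1: 105 enrolled. Synopsis: at least 100 implanted eyes, one study eye per subject. Section 8.1: p0 = 0.925, true p = 0.85, one-sided alpha 0.05. The non-implantation rate r is not given in the readable documents; 2% to 8% is an assumption.

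**1. Reproduce the plan's power.** For n eyes, let c be the largest count with P(X ≤ c | n, 0.925) ≤ 0.05. Power is P(X ≤ c | n, 0.85), the chance of declaring the rate below 0.925 when it is truly 0.85. At n = 100, c = 87, the attained level is 0.0364 and power is 0.7527, matching the stated 0.753. All eight rows of the 8.1 table (n = 100 to 170) match to three decimals.

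**2. Margin.** 105 − 100 = 5, and 5/105 = 4.8%. Six non-implanted subjects leave 99 eyes.

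**3. Chance of a shortfall at 105 enrolled.** With non-implanted ~ Binomial(105, r), P(implanted < 100) = P(at least 6 not implanted).

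| Assumed r | Expected implanted, 105 × (1 − r) | P(fewer than 100) |
|---|---|---|
| 2% | 102.9 | 0.02 |
| 3% | 101.9 | 0.10 |
| 5% | 99.8 | 0.43 |
| 8% | 96.6 | 0.85 |

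This takes subjects as independent and closure at exactly 105. It leaves out anyone enrolled but still awaiting surgery at closure, and it leaves out later dropout, which does not reduce the number of implanted eyes.

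**4. Effect on power.** Same exact test at other counts:

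| Implanted eyes | Critical count c | Attained level | Power |
|---|---|---|---|
| 94 | 82 | 0.0486 | 0.769 |
| 95 | 82 | 0.0252 | 0.683 |
| 99 | 86 | 0.0339 | 0.740 |
| 100 | 87 | 0.0364 | 0.753 |
| 105 | 91 | 0.0254 | 0.724 |

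Power is not monotone because the test is discrete. Ninety-four eyes give more power than 100, and 105 give less. The 8.1 statement that at least 100 subjects provide at least 75% power therefore fails at n = 105, even if all 105 are implanted.

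**5. Enrolment needed under a count of implanted eyes.** For an expected 100, 100/(1 − r) rounded up gives 103, 104, 106 and 109 at r = 2%, 3%, 5% and 8%. For a 90% chance of at least 100, the numbers are 104, 105, 108 and 113.

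**The case against.** **The criterion compels nothing.** It is one permissive ground under a general right to stop. This stands: 4.7.1 is not a binding stopping rule. But it is the only listed ground tied to study size, so its unit still matters.

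**The 44-exchange condition narrows the exposure.** With 99 implanted eyes it needs an exchange rate of at least 44/99 = 44%, with all those exchanges already past the 3 Month Visit. If exchanges accrue more slowly, enrolment may run past 105 and the shortfall shrinks. This stands as a limit on likelihood, and the probabilities above apply only to closure at 105. It does not put 100 implanted eyes into the criterion.

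**Section 4.7.2 already watches the sample size.** True in part, but 4.7.1 does not make closure depend on that review.

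**The rationale for 105 may be redacted.** Sample-size text in the Synopsis is blacked out, and SAP Section 6 is not in the readable text. The margin therefore cannot be called unjustified. An explanation there would still leave the unit in 4.7.1 as it is.

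**Two stronger readings are not supported.** A reader might infer that closing short means falling below 75% power. Step 4 shows no such uniform loss: some counts below 100 have more power, and 105 itself falls below 75%. A reader might also infer that recently implanted subjects would be placed in Cohort 1 by calendar date whatever their outcome. No section says this. Section 4.7.1 also promises appropriate follow-up, and 6.4 describes the right as one to stop enrolment, which is compatible with those subjects reaching their 3 Month decision. The text is ambiguous, no more.

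**Conclusion.** The unit mismatch is real and can be read directly from 3.3.1, 4.5, 4.7.1 and the Synopsis. The closing criterion can be satisfied with fewer than 100 implanted eyes once six or more of 105 enrolled subjects are not implanted. Whether this is likely depends on a rate the documents do not give. It is remote at 2%, close to even at 5% and probable at 8%, if the study closes at 105.

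The consequence is a missed minimum count in a feasibility study, with a modest and irregular effect on power. The conflict in wording over what termination means for implanted subjects awaiting the 3 Month decision is a separate matter of reconciliation.

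**What to change.** In Protocol 4.7.1, restate the first condition as a number of eyes implanted with the HMIOL, set no lower than the required 100, and keep the 44-exchange condition. Use the same unit in 8.1. State the exact power at the number chosen instead of relying on 75% at every n of 100 or more: 100 eyes give 0.753, 105 give 0.724 and 110 give 0.785 (the protocol's own table). If the number is also meant to cover later loss to follow-up, state the assumed rate, since Section 8.3 allows no imputation.

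Separately, reconcile 4.7.1, 6.4 and 3.3.4 so that they say the same thing about subjects already implanted who have not reached the 3 Month decision, including whether access to exchange continues. Which rule applies is for the sponsor and investigators to settle.

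The cost is a short wording change and at most a few more subjects. At an assumed 5% or 8% non-implantation, the expected enrolment for 100 implanted eyes is 106 or 109, well within the 200 allowed.

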4.7.2 STUDY EXTENSION

After the first 25 subjects have reached the 3 month time point (and every 25 subjects thereafter), subject accountability and the rate of optic exchanges will be evaluated, and the enrollment goal will be reevaluated with respect to achieving the necessary sample size.

4.8 CONCOMITANT THERAPIES

4.8.1 CONCOMITANT MEDICATION

Concomitant medications are any prescription drugs used by a subject until conclusion of study participation. Any medication the Investigator deems in the best interest of the subject, is acceptable to prescribe or administer. However, any and all are to be recorded in both the Concomitant Medication source document and eCRF as well as the reason for use (indication). An AE is to be reported and/or recorded as appropriate (see Section 6.0).

4.8.2 CONCOMITANT PROCEDURES

A concomitant procedure is any invasive or non-invasive ocular or peri-ocular procedure that takes place during study participation and will be captured in both the Concomitant Procedure Source Document and eCRF. The following are examples of two such procedures:

- Any PO surgical adjustments to Fellow Eye (i.e. corneal refractive surgery, lens exchange, etc.
- Neodymium: Yttrium-aluminum-garnet (Nd:YAG) procedure to treat Posterior Capsule Opacification (PCO), if necessary. This will be listed as "Nd:YAG Capsulotomy."

Note: Any Nd:YAG capsulotomy procedures prior to exit will be performed only in response to spontaneous subject complaints (i.e. not solicited by study personnel) of reduced Visual Acuity (VA) or glare that affects functional vision, which is associated with PCO or striae, and captured on the eCRF in SLE findings.

CLARVISTA MEDICAL

PROTOCOL CP-00001 Rev.05

An AE is to be reported and/or recorded as appropriate (see Section 6.0). Any procedure reported in the Concomitant Procedure eCRF must have a corresponding Indication listed in either the Ocular History or AE eCRF (Only exception: PCO – See Section 6.1 for further details).

4.9 PROTOCOL DEVIATIONS

All protocol deviations, the date of deviation, and reason will be documented in the Source Document and eCRF. All deviations will be categorized as either major or minor in the following manner:

Major:

- Deviations impacting subject safety
- Deviations impacting subject rights
- Deviations impacting data integrity

Minor:

- All other deviations (e.g. out of window visits, missed data point, etc.)

All major deviations must be reported by the Investigator to the Sponsor and IRB/EC immediately. Subject assessments will continue per protocol for the duration of planned participation unless the deviations put the subject at risk or the subject's condition requires that he/she be discontinued from the study.

5.0 STUDY MATERIALS

5.1 DESCRIPTION OF TEST ARTICLE

The HARMONI™ Modular Intraocular Lens (HMIOL) System is an investigational device designed to allow safe exchange or adjustment of an IOL optic after implantation. [REDACTED]

[REDACTED]

[REDACTED]

[REDACTED]

CLARVISTA MEDICAL

PROTOCOL CP-00001 Rev.05

The optic component is available in 16 D to 26 D Spherical Equivalent (SE) powers in 0.50D increments. All components are sterilized using ethylene oxide (EtO) and has a shelf life 1 year from the date of sterilization.

[REDACTED]

- [REDACTED]
- [REDACTED]

5.1.1 INSTRUCTIONS FOR USE – STUDY EYE

Refer to the Surgical Guide for all use and administration details.

5.2 FELLOW EYE INTRAOCULAR LENS

Fellow Eyes will be implanted with a commercially available IOL.

5.2.1 INSTRUCTIONS FOR USE – FELLOW EYE

Refer to the appropriate product insert Instructions for Use documents for all use and administration indications, warnings, and limitations for commercially available products. *No "Off-Label" product use will be allowed.*

5.3 PACKAGING AND LABELING

All packaging and labeling will be consistent with the current study design. The labeling will include at a minimum, the following:

- Sponsor name and address
- Study number
- "For Single Use Only" statement (or equivalent symbol)
- "Investigational Device" caution statement
- Sterility symbol
- Storage temperature range requirements or equivalent (e.g. "Store at room temperature.")
- Expiration date
- Power designation
- Unique serial number
- Model number

5.4 ACCOUNTABILITY

The Investigator is responsible for keeping accurate accountability records of the number of study lenses received, dispensed, and returned to Sponsor. The study lenses must be stored under the appropriate conditions in a secure area and are to be implanted only in subjects enrolled in the study, in accordance with the conditions specified in this protocol.

All accountability records will include the following:

- Model and serial numbers

CLARVISTA MEDICAL

PROTOCOL CP-00001 Rev.05

- Receipt date
- Quantities received
- Initials (attributability) of site personnel who received, dispensed, or returned study lenses
- Date of use
- Subject treated with the study lens (by Subject ID and Initials only)
- Date returned to Sponsor
- Defective or damaged study devices

Periodically throughout the study and/or upon completion, the Sponsor (or designee) will review and verify the Investigator's accountability records. Following verification, and as directed by the Sponsor, all unused and explanted products must be returned to the Sponsor.

Note: In addition, any study lenses or components deemed defective, damaged, malfunctioning, or explanted must be retained by the site and returned to the Sponsor for evaluation. Under no circumstances are any components to be discarded or otherwise disposed of. If there is any question as to the applicability of this directive, consult the Protocol Contacts page of this protocol and discuss the situation with a Sponsor representative.

5.5 OTHER MATERIALS

Additional materials can be provided to sites for the duration of the study on an as-needed basis and may include:

- ETDRS light box, glare source, and charts to perform the standardized VA assessments described in the Manual of Procedures
- Medical injectors (for study lens injection only)
- IOL micro-incision cutter and forceps
- 40 cm measuring tool to perform near vision testing
- Konan Specular Microscope
- Pentacam Anterior Segment Imaging System

6.0 ADVERSE EVENTS

Safety assessments include adverse events/serious adverse events, and adverse device events. The reporting time period is from the time of consent through the last study visit (12 Month Visit post-primary cataract extraction for Cohort 1 and post-optic exchange for Cohort 2).

6.1 DEFINITIONS

6.1.1 ADVERSE EVENT (AE)

An AE is any untoward medical event in a subject that does not necessarily have a causal relationship to the study device or protocol. AEs include Adverse Device Effects (ADEs). Conditions or diseases that are chronic but stable should not be recorded on AE pages of the eCRF. Similarly, changes in a chronic condition of disease that are consistent with natural disease progression are NOT adverse events and also should not be recorded on the AE pages of the eCRF.

Refer to Section 6.3.1 for instructions regarding events that require expedited reporting to the Sponsor and IRB/EC.

Experience with cataract surgery and the implantation of IOLs has shown that some conditions can be considered normal or expected events following these procedures. The following may be considered normal or expected events after cataract surgery and only need to be reported as AEs as specified here:

- Iritis (cell / flare) – if treated
- Persistent Corneal Stroma Edema (if present at 1 Month)
- Increased IOP only if medical/surgical intervention is required (i.e. medication, paracentesis manipulation)
- VA decrease of 10 or more letters (2 lines) from any previous visit not secondary to any underlying condition
- Any expected post-operative ocular event requiring a change in standard postoperative medication regimen

Note: PCO is not to be reported as an AE, as per ISO 11979-7:2014.

Particular attention should be paid to ensure timely and accurate reporting of any of the following cataract surgery related events:

- Endophthalmitis
- Capsular injury
- Vitreous loss
- Macular edema
- Retinal detachment
- Lens dislocation
- Moderate to severe corneal edema
- Pupillary block / angle closure
- Hypopyon or hyphema

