8.3.1 SAFETY OUTCOMES

8.3.1.1 ADVERSE EVENTS AND DEVICE DEFICIENCIES

Adverse events and device deficiencies will be summarized at each study visit based on the safety population for Cohort 1 and Cohort 2. The number and percentage of eyes reported with the ISO specified 12-month cumulative and persistent adverse events will be calculated for Cohort 1 and Cohort 2 separately. Additionally the events will be summarized for the HMIOL cohort (12-months after primary cataract surgery for Cohort 1 and 12-month after HMIOL optic exchange for Cohort 2). The corresponding one-sided lower 95% confidence limit will be calculated based on the binomial distribution and compared to the ISO SPE rate. If the one-sided lower 95% confidence limit is smaller than the SPE rate specified by ISO, then the null hypothesis of event rate of less than the SPE rate will not be rejected.

[REDACTED]

The ISO cumulative and persistent adverse events will also be provided for the fellow eye cohort and numerically compared to those of HMIOL eye cohort.

Additionally, the number and percentage of eyes reported with HMIOL-related adverse events during the study will be summarized for HMIOL Cohort 1, HMIOL Cohort 2, and HMIOL-eye Cohort. The two-sided 90% confidence interval of the percentage will also be provided.

8.3.1.2 [REDACTED]

[REDACTED]

[REDACTED]

[REDACTED]

[REDACTED]

[REDACTED]

[REDACTED]

[REDACTED]

[REDACTED]

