5.4. Safety Endpoints

All HMIOL Eyes Cohort

- [Redacted]
- [Redacted]
- Adverse event rates as compared to ISO 11979-7:2014 Annex B Safety and Performance Endpoint (SPE) tables including SSIs
- [Redacted]

Cohort 1 (No-Optic Exchange)

- [Redacted]
- AE rates as compared to ISO 11979-7:2014 Annex B Safety and Performance Endpoint (SPE) tables including SSIs
- [Redacted]

Cohort 2 (Optic Exchange)

- [Redacted]

Protocol CP-00001

ClarVista Medical, Inc.

A hypothesis test for this endpoint will be performed to assess whether mean percent change in ECC is no worse than 14%. The null and alternative are stated as:

$$H_0: \mu \geq 14\%$$

$$H_A: \mu < 14\%$$

Where μ represents the mean percent ECC loss from pre-exchange (3 months after the primary cataract surgery) to 3-month post-exchange for the eyes with HMIOL optic exchange (6 months after the primary cataract surgery). This test will be based on a one-sided, one-sample 0.05 t-test of a mean.

- [REDACTED]
- [REDACTED]
- AE rates as compared to ISO 11979-7:2014 Annex B SPE tables (includes SSIs –optic exchange procedures due to targeted residual refractive error are excluded)
- [REDACTED]

Fellow Eye Cohort

- [REDACTED]
- AE rates as compared to ISO 11979-7:2014 Annex B SPE tables including SSIs
- Dilated fundus examination

Adverse event rates in this study will be assessed as outlined in ISO 11979-7:2014 Annex B for posterior chamber IOLs. Following this methodology, for each specified adverse event we will calculate an exact lower one-sided 95% confidence bound for the proportion of eyes with the event at the one-year time point. As described in ISO 11979-7:2014 Annex B.3-B.4, success is defined as a lower bound that is less than the safety and performance endpoint (SPE) rate for that adverse event, in other words failing to reject the hypothesis that the event rate is greater than the SPE rate. The SPE rates for posterior chamber IOLs are provided in Table 1 below.

Table 1: Rates of Specific Adverse Events as Outlined in ISO 11979-7:2014 Annex B:

Adverse Event	Incidence Threshold
Cumulative	
Cystoid macular edema	3.0%
Hypopyon	0.3%
Endophthalmitis (inflammatory reaction (sterile or infectious) involving the vitreous body	0.1%
Lens dislocated from posterior chamber	0.1%
Pupillary block	0.1%
Retinal detachment	0.3%
Secondary surgical intervention (excluding posterior capsulotomies)	0.8%
Persistent	
Corneal stroma edema	0.3%

Protocol CP-00001

ClarVista Medical, Inc.

Cystoid macular edema	0.5%

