Iritis	0.3%
Raised IOP requiring treatment	0.4%

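### Iritis need be reported as an AE only if treated, yet the persistent-iritis benchmark has no treatment condition, so the comparison can be biased toward passing

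*Protocol*

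**What the plan says.** Protocol 6.1.1 lists conditions that may be regarded as normal or expected after cataract surgery and that "only need to be reported as AEs as specified here". The iritis entry is "Iritis (cell / flare) – if treated". The raised-pressure entry is "Increased IOP only if medical/surgical intervention is required". Neither entry is limited to a particular period after surgery.

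SAP Table 1 (Section 5.4) lists iritis under the persistent events at 0.3%, without qualification. The next row, at 0.4%, is "Raised IOP requiring treatment".

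On the analysis, Protocol 8.3.1.1 states: "The number and percentage of eyes reported with the ISO specified 12-month cumulative and persistent adverse events will be calculated". SAP 5.4 presents the endpoint as adverse event rates compared with the ISO tables and says "we will calculate an exact lower one-sided 95% confidence bound for the proportion of eyes with the event at the one-year time point". It adds that "success is defined as a lower bound that is less than the safety and performance endpoint (SPE) rate for that adverse event".

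Slit lamp results are summarised descriptively (Protocol 8.3.1.3, SAP 5.5). Neither document defines persistent iritis or names the record from which it is counted.

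**The concern.** The numerator and the benchmark appear to use different case rules. An eye with cell or flare at 12 months that nobody treats meets the SAP's row label as printed, but the protocol does not oblige the site to report it as an adverse event. A count built from adverse event reports can then omit it, while the 0.3% limit it is compared with is not restricted to treated eyes.

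The direction is fixed: leaving out a case can only lower the observed rate and its lower bound, and success means a low lower bound. The limit is also so small relative to the sample size that one or two eyes settle the outcome. SAP Section 1 says the results are meant to support a future confirmatory study, so an iritis rate that depends on who happened to be treated would carry forward into that planning.

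**Working it through.** **Step 1. Is iritis the only persistent row with this problem?** The reporting rules in Protocol 6.1.1 against the SAP Table 1 rows:

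| Persistent event | SPE rate | Treatment condition in SAP row | Treatment condition in protocol reporting rule |
|---|---|---|---|
| Corneal stroma edema | 0.3% | none | none (reportable if present at 1 month) |
| Cystoid macular edema | 0.5% | none | none (macular edema is on the list for particular attention) |
| Iritis | 0.3% | none | yes |
| Raised IOP | 0.4% | yes | yes |

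Only iritis has a reporting rule narrower than the row it is compared with. The catch-all entry in 6.1.1 does not close the gap, because it depends on a change to the postoperative medication regimen and so is also tied to treatment.

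**Step 2. How many eyes decide the comparison?** Inputs: SPE rate 0.003 (SAP Table 1); exact one-sided 95% lower bound, with success if it is below the SPE rate (SAP 5.4); 100 to 200 eyes (Protocol synopsis, sample size); at least 44 exchanges for Cohort 2 (Protocol 4.7.1). The plan gives no operating figure of its own for this comparison, so there is none to reproduce.

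The bound L for x cases in n eyes solves P(X ≥ x | n, L) = 0.05, so L is the 5th percentile of Beta(x, n − x + 1). For x = 1 this is L = 1 − 0.95^(1/n); with n = 100, 1 − 0.95^0.01 = 0.00051.

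| Eyes | Cases counted | Lower bound | Against 0.3% |
|---|---|---|---|
| 44 | 1 | 0.12% | pass |
| 44 | 2 | 0.81% | fail |
| 100 | 1 | 0.05% | pass |
| 100 | 2 | 0.36% | fail |
| 200 | 2 | 0.18% | pass |
| 200 | 3 | 0.41% | fail |

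At each size the smallest failing count becomes a pass when one eye is left out.

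**Step 3. What could this do to the chance of a flag?** This needs two figures that the documents do not give: the true rate of persistent iritis, and the share f of cases that is treated and so reported. Both are assumed here for illustration. With r the smallest failing count (2 of 100, 3 of 200), the chance of failing the benchmark is P(X ≥ r | n, f × true rate). For example, with n = 100, a true rate of 2% and f = 0.5, it is 1 − 0.99^100 − 100 × 0.01 × 0.99^99 = 0.264.

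| True rate (assumed) | f (assumed) | n = 100 | n = 200 |
|---|---|---|---|
| 2% | 1 | 0.597 | 0.765 |
| 2% | 0.5 | 0.264 | 0.323 |
| 2% | 0.25 | 0.090 | 0.080 |
| 3% | 1 | 0.805 | 0.941 |
| 3% | 0.5 | 0.443 | 0.579 |
| 3% | 0.25 | 0.173 | 0.191 |

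If every case is treated (f = 1), nothing is lost. The loss grows as f falls.

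**The case against.** A reader might infer that untreated iritis at 12 months can never be an adverse event and is certain to be left out. The text does not go that far. The list in 6.1.1 covers conditions that may be considered expected; an investigator could decide that iritis a year after surgery is not one of them and report it under the general adverse event definition. The SAP, which supersedes the protocol's analyses, speaks of the "proportion of eyes with the event at the one-year time point" and does not restrict the count to adverse event forms. Counting a case found at the slit lamp is therefore compatible with the SAP. What remains is that nothing requires it: the iritis entry has no time limit, the endpoint is headed as adverse event rates, and slit lamp findings are not linked to the count. Sites and analysts could follow the plan faithfully and reach different numerators.

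It can also be said that the 0.3% row is a short label from a standard that is not reproduced here, and that the standard's case definition might differ. That is fair. The point rests only on the SAP's own table; if a treatment condition is intended, the SAP should state it.

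A third objection is that counting any trace of cell or flare could make the numerator broader than the benchmark. This stands, and it is why the fix needs a case definition.

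Finally, the study is a feasibility trial whose formal tests are not meant to be definitive (SAP Section 4), and abnormal findings may be line-listed (SAP 5.5). That limits the consequence, but the SAP still declares success or failure on this row.

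**Conclusion.** The mismatch between the reporting rule and the benchmark row is in the text, and its possible effect runs only toward passing. The plan as written permits an under-count; it does not establish that one will occur. The size is unknown, because the documents give neither a rate of iritis at 12 months nor the share that goes untreated, and the probabilities in step 3 of the working rest on assumed values. What does not rest on assumption is the sensitivity: with 44, 100 or 200 eyes, one omitted eye is enough to turn the smallest failing count into a pass. A reader might suppose that two or three eyes would have to be missed to reverse the result; the bounds show that one can suffice.

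The rule should be changed before analysis, since the examination needed to close the gap is already scheduled at 12 months in both HMIOL cohorts (Appendix A, Tables 1 and 3).

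**What to change.** 1. In SAP 5.4, define persistent iritis for the SPE comparison as iritis present at the 12-month visit (after primary surgery for Cohort 1, after exchange for Cohort 2), whether or not treated. Identify it from the scheduled 12-month slit lamp examination using a pre-specified case definition, such as a minimum cell or flare grade consistent with the benchmark.
2. In Protocol 6.1.1, state that the treatment limit on reporting iritis does not govern this count. It can stay for routine adverse event reporting.
3. Use the same ascertainment for fellow eyes where a slit lamp record exists. SAP 5.4 also compares those eyes with the SPE rates, and Protocol 8.3.1.1 compares them numerically with the HMIOL eyes. Appendix A Table 2 shows no visible slit lamp row, though some of its rows are redacted, so availability cannot be confirmed here. If there is no such record, state that the fellow-eye iritis rate is not comparable.

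Cost: SAP wording plus one line of Protocol 6.1.1, with no added visit or examination for HMIOL eyes and no change to how iritis is managed. The reported iritis rate may rise slightly.
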